9. EFFICACY ANALYSIS

Unless otherwise stated, the ITT analysis population will be used for efficacy analyses. Due to the open-label nature of the trial and the lack of a control group, efficacy data at all scheduled visits will be summarized and no formal statistical hypothesis testing will be performed.

Certain related endpoints relying on the same fundamental measurement may result in analyses that are continuous in one case and categorical in another case. For example, CDAI scores are the fundamental measurement for the CDAI Change from Baseline endpoint that is described in Section 9.3, and CDAI Change from Baseline is a continuous analysis. On the other hand, CDAI scores are the fundamental measurement for the CDAI Clinical Remission endpoint described in Section 9.4, and the proportion of remitters at a given visit is a categorical analysis.

All efficacy endpoints will be tabulated by scheduled visit.

9.1. Treatment Failure Rules

Final Treatment Failure status will be determined by internal clinical review using the following rules:

1. Any protocol-prohibited change in CD medications including the following:
 - a. Post-baseline initiation of, or increase in, corticosteroids to treat worsening CD to a dose greater than the maximum daily dose taken between the Screening and Baseline visits
 - b. Prolonged course of systemic corticosteroids > 14 days for treatment of disease other than CD
 - c. Initiation of an immune-suppressing therapy including 6-mercaptopurine (6-MP), azathioprine, anti-TNF agents, or vedolizumab
 - d. Post-baseline initiation of antibiotics to treat worsening of CD/disease flare
2. Surgical resection of small intestine or colon during the study as a treatment of CD-related symptoms
3. Endoscopic dilation treatment for CD-associated stricture(s) during the study

Treatment failures at Week 12 and Week 52 will be determined by using the above rules. Treatment failure status will be used as a criterion in NRI. Patients identified as Treatment Failures will be listed.

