8.3. Trial Discontinuation

Patients will be encouraged to complete the trial; however, they may voluntarily withdraw at any time. The Investigator will provide a written explanation in the source documentation to be entered on the appropriate eCRF page describing the reason for discontinuation.

The criteria for enrollment are to be followed explicitly. If a patient who does not meet enrollment criteria is inadvertently enrolled, the Medical Monitor must be contacted, and that patient will be withdrawn from the trial if continuation is determined to be a safety risk.

Reasons for discontinuation include, but are not limited, to the following:

- Physician decision: The Investigator must discontinue investigational drug if it is determined that it is not safe or in the patient's best interest to receive further treatment. The Medical Monitor should be promptly notified of the decision
- Non-compliance with investigational drug: After consultation between the Investigator, the Medical Monitor, or Clinical Monitor, and the Sponsor when appropriate, a patient may be discontinued from the trial for failure to comply with dosing regimen as specified by the protocol
- Non-compliance with protocol/protocol deviation: A patient fails to follow protocol procedures, or other event or decision that stands in contrast to the guidelines set in the protocol
- Adverse event: A patient must be discontinued from investigational drug if, in the judgment of the Investigator or if specified in the protocol, the patient develops an AE such as an intercurrent illness or complication that justifies discontinuation of investigational drug
- Lack of efficacy: Decision by the patient and/or the Investigator to discontinue treatment due to a lack of expected or desired effect related to a therapy
- Withdrawal by Patient: The patient may choose to discontinue investigational drug at any time. Every effort should be made within the bounds of safety and patient choice to have each patient complete the Early Termination Visit and 30-day and 90-day Safety Follow-up Visits. If a patient withdraws consent, the only additional trial data to be collected will be the follow-up of SAEs as mandated by the protocol
- Pregnancy: If the patient becomes pregnant investigational drug must be discontinued (see Section 12.2.11)
- Trial termination by Sponsor
- Other

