5.5.3. Visit Windows

The analysis time point assignment for the post-baseline visits will be assigned based on the analysis windows described in [Table 4](#) below for the following items:

- Efficacy (please see Protocol Table 2 for a description of what study elements are considered to belong to the Efficacy category; it is also noted that not all Efficacy elements are considered in this SAP, please see the endpoints in Sections 4.2.2, 4.2.3, and 12)
- 12-lead ECG
- Vital signs
- Hematology
- Blood chemistry
- Pregnancy test
- Urinalysis
- Physical examination
- Pulmonary function test
- Optical coherence tomography

Adverse events and coagulation panel data will not be windowed.

If multiple assessments are available within a range, then the one closest to the target day will be used for that analysis time point. If multiple assessments are same distance, but on different sides of the target day, then the latter one will be used. If multiple assessments are available on the same day, then the average of these assessments will be used, except for the lab and ECG data for which the assessment at a later time of the same day will be used.

Table 4. Analytic Visit Windows

Visit	Ideal Analysis Day^a	Visit Window
Baseline	1	<= 1
Week 4	29	2 – 42
Week 8	57	43 – 70
Week 12	85	71 – 98
Week 24	169	99 – 210
Week 36	253	211 – 294
Week 48	337	295 - 350
Week 52	365	351 - 392
Week 64	449	393 - 490
Week 76	533	491 - 574
Week 88	617	575 - 658

Week 100	701	659 - 742
Week 112	785	743 - 826
Week 124	869	827 - 910
Week 136	953	911 - 994
Week 148	1037	995 - 1078
Week 160	1121	≥ 1079
Safety Follow-up Day 30	30	≤ 60
Safety Follow-up Day 75 and Day 90	90	≥ 61

^aExcept for the visits recorded as safety follow-up visits, the reference date will be the date of the first dose of IP in the study, and the relative day is calculated date of assessment/collection – date of the first dose of IP + 1 if the date of assessment/collection is on or after the date of the first dose of IP, or date of assessment/collection – date of the first dose of IP if the date of assessment/collection is before the date of the first dose of IP. The reference date for the visits recorded as safety follow-up visits will be the date of the last dose of IP in the study, and the relative day is calculated date of assessment/collection – date of the last dose of IP.

Applying above visit window rules will be done after distinguishing treatment visits and follow-up visits by CRF visit labels.

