5.5.4. Handling of Missing and Partial Data

For all proportion-based efficacy endpoints, patients with missing efficacy data and the responses after treatment failure will be considered non-responders (NRI) in the primary analyses.

Treatment failures at Week 12 and Week 52 will be determined based on the rules listed in Section 9.1. In all analyses where NRI is used, responses of the patients who are treatment failures at Week 12 will be imputed as non-responder at Week 12 and onwards. In addition, responses of the patients who are treatment failures at Week 52 will be imputed as non-responder at Week 52 and onwards.

Continuous efficacy endpoints will not be imputed.

Sensitivity analyses on missing data on selected endpoints are detailed in the efficacy analyses sections 9.1 and 9.2.

With the exception of partial dates, missing demographic, disposition, baseline characteristics, medical history, and safety data will be analyzed using observed data only, without imputation. For

partial dates, the algorithms for imputation will vary depending upon the parameter; the details can be found in [Appendix 1](#).

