APPENDIX 5. DOCUMENT REVISION HISTORY

Version	Date	Notes/Revisions
1.0	March 03 2016	Initial version.
1.1	November 23 2016	Updated with details and additional analyses.
1.2	January 26 2017	Updated with details on missing data and other details.
1.3	June 1, 2018	
Updated to reflect the Week 12 and Week 52 summary tables generated for topline analyses, definition of treatment failure, as well as to reflect endpoint alterations and additional details regarding CDAI, SES-CD, GHAS, and RHI algorithms. Analysis of compliance rate categories has been excluded.
 
Following endpoints have been removed from the SAP
 
 • PRO CD SF+AP response-25 • PRO CD SF+AP response-50 • PRO CD SF+AP response-30 + 2P • PRO2 CD response-25 • SF&AP clinical response-2 • SF&AP clinical response-1 • Endoscopic remission-2 • Histologic improvement • Histologic response 
Following endpoints have been added to the SAP
 
 • CRP-response-10 • FCP response-250 • Fistula Response • GHAS Improvement • GHAS Remission • RHI Improvement • RHI Response • RHI Remission • Global RHI Score • RHI Mucosal Healing
1.4	August 28, 2019	
LOCF removed.
 
Treatment Failure rule is used in NRI
 
Efficacy graphs added

1.5	January 06, 2020	
Changes from data review meeting
 
 • PFT abnormality has been revised • Missing segment imputation of SES-CD has been added

		
• Lower bound of 0 for Hematocrit sub-score of CDAI has been added• Treatment failure criteria has been revised• RHI response analysis on all patients has been removed• RHI remission by segment for subset of segment score > 3 is replaced by RHI remission by segment for non-RHI remitters• CRP Change among patients having CRP \geq 10 mg/L at Baseline has been added• Analysis window has been added to Safety follow-up visits• Unscheduled and early termination visits are included in all analysis windows• Patients requiring cardiac monitoring is determined programmatically• Listing of non-trial procedures added• Section on PK analysis is removed and combined with Section on PD• Description of SDTM data in Section 5 is removed
--	--	---

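### SAP 9.1 has no failure rule for stopping RPC1063 for lack of efficacy, so an in-window Early Termination visit can make such a patient an NRI responder

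*SAP*

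**What the plan says.** **When NRI applies.** SAP 5.5.4 states that, for proportion endpoints, "patients with missing efficacy data and the responses after treatment failure will be considered non-responders (NRI) in the primary analyses". SAP 9.4 makes NRI the primary analysis of every binary endpoint, with an observed-case analysis as the sensitivity analysis.

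**What a treatment failure is.** SAP 9.1 opens with "Final Treatment Failure status will be determined by internal clinical review using the following rules". Three kinds of event follow: protocol-prohibited changes in Crohn's medication, surgical resection, and endoscopic dilation. It closes with "Treatment failures at Week 12 and Week 52 will be determined by using the above rules". Discontinuation of the drug is not listed, for any reason.

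**Withdrawal.** Protocol 8.3 gives as one reason for stopping "Lack of efficacy: Decision by the patient and/or the Investigator to discontinue treatment due to a lack of expected or desired effect". Protocol 7.1 requires an Early Termination visit after such a withdrawal. Protocol Tables 2 and 3 schedule the CDAI and, subject to a colonoscopy waiver, the SES-CD at that visit. Protocol 8.3 lets alternative treatment begin once the visit is done.

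**Visit windows.** SAP 5.5.3 assigns assessments by study day. On exclusions it says only "Applying above visit window rules will be done after distinguishing treatment visits and follow-up visits by CRF visit labels". The version 1.5 entry in SAP Appendix 5 records that "Unscheduled and early termination visits are included in all analysis windows". Where a window holds several assessments, "If multiple assessments are available within a range, then the one closest to the target day will be used for that analysis time point".

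**The concern.** The SAP already treats some events after baseline as non-response even when a value was measured. Starting an antibiotic for a flare is one. Taking the patient off the drug because it has not worked is not handled in the same way, and nothing in 5.5.4 or 9.1 says that this was deliberate. Version 1.5 both revised the failure criteria and put Early Termination visits into the windows, so the two provisions now interact and the text does not address the result.

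At stake is what the response and remission rates mean. A reader of an NRI analysis would normally assume that patients withdrawn for lack of effect are in the non-responder count. With one arm, no control rate shows how much of the reported figure depends on this choice. The planned observed-case analysis does not expose it either, because nothing in its description removes the same Early Termination value.

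**Working it through.** **1. Windows (SAP Table 4).**

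| Visit | Ideal day | Window | Opens before ideal day |
|---|---|---|---|
| Week 12 | 85 | 71-98 | 85 - 71 = 14 days |
| Week 24 | 169 | 99-210 | 169 - 99 = 70 days |
| Week 52 | 365 | 351-392 | 365 - 351 = 14 days |

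A patient who stops before Day 71 and has the Early Termination visit then has no Week 12 value and is a non-responder. A patient whose visit falls on Day 71 or later has a value.

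**2. Is there a value to score?** The CDAI diary and clinical score are scheduled at Early Termination. In Induction, colonoscopy is waived only if one was done within 8 weeks (56 days). The screening colonoscopy precedes Day 1, so by Day 71 it is at least 70 days old. The waiver therefore applies only if the Week 12 colonoscopy has been done. In the Extension, an Early Termination visit on Days 351-392 without a Week 52 colonoscopy also calls for one. Endoscopic response can thus be reached by the same route as CDAI response.

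**3. Can such a patient meet the criterion?** Take a CDAI that goes from 430 to 325. The fall is 430 - 325 = 105, which is at least 100 and so a CDAI clinical response (SAP Table 3). The score of 325 still lies in the moderate band of 220 to 450 (SAP 4.2). Withdrawal rests on clinical judgement and is not tied to the endpoint definitions, so response and withdrawal for lack of efficacy can occur together.

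**4. Week 24.** Protocol Table 2, footnote c, allows patients who do not go on to the Extension up to 4 weeks after Week 12 for the Early Termination visit: nominally 84 + 28 = Day 112. Day 99 or later falls in the Week 24 window. A patient who never entered the Extension can therefore supply a Week 24 response. Colonoscopy is waived within 8 weeks of the Week 12 examination, so at that point the route is open mainly for the symptom-based endpoints.

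**5. Nearest assessment.** With a scheduled Week 12 visit on Day 82 and Early Termination on Day 86, the distances from Day 85 are 3 and 1. The Early Termination value replaces the scheduled one.

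**6. Size.** The plan's precision figures reproduce first. The half-width is 1.96 × sqrt(p(1 - p)/n):
- n = 30: 12.8 points at p = 0.15 and 16.4 at p = 0.30.
- n = 60: 9.0 points at p = 0.15 and 11.6 at p = 0.30.

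SAP 5.4 uses the same population in both periods, so with n = 60 each patient is worth 1/60 = 1.7 points at any visit. The number affected, k, is not in the documents; 1 to 5 is assumed. The table recodes k such patients from responder to non-responder, starting from the planning rates (0.30 × 60 = 18 and 0.15 × 60 = 9). Intervals are Clopper-Pearson, as in SAP 9.4.

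| k | Response, % (95% CI) | Remission, % (95% CI) |
|---|---|---|
| 0 | 30.0 (18.8-43.2) | 15.0 (7.1-26.6) |
| 1 | 28.3 (17.5-41.4) | 13.3 (5.9-24.6) |
| 2 | 26.7 (16.1-39.7) | 11.7 (4.8-22.6) |
| 3 | 25.0 (14.7-37.9) | 10.0 (3.8-20.5) |
| 5 | 21.7 (12.1-34.2) | 6.7 (1.8-16.2) |

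**The case against.** **The rules have their own logic.** A reader might infer that SAP 9.1 is upside down, penalising a weak sign of failure and ignoring the direct one. The documents do not support that. Nearly every listed event is an intervention that could itself have produced the outcome, and the rule on prolonged steroids for other diseases is not a sign of Crohn's failure at all. Withdrawal alone does not contaminate the Early Termination score, because alternative treatment follows the visit. Scoring the measured value is a defensible estimand, so calling the result biased presupposes the other one. This stands, but the SAP does not state that it has chosen this estimand.

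**The SAP is already stricter than the protocol.** Protocol 13.2.1 plans no imputation. True, but that does not settle how NRI, once adopted, should treat these patients.

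**The exposed group is narrow.** Many stopping decisions come at the end of Induction, when a scheduled Week 12 assessment normally exists and may properly be counted. This stands, and it limits the size of the problem.

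**Later rescue might trigger the medication rule.** It might. But SAP 9.1 gives no cut-off date for failure at Week 12 or Week 52, and this protection would depend on rescue and on the internal review, not on the withdrawal.

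**The text is incomplete.** SAP 9.4 breaks off at Table 6 in the available copy and 9.5 is not shown. A further rule there cannot be excluded.

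**Conclusion.** The gap is real and modest. As 5.5.4, 5.5.3 and 9.1 read together, a patient withdrawn for lack of efficacy can be an NRI responder at Week 12, 24 or 52 through an in-window Early Termination visit. This requires that the numeric criterion is met and that no scheduled assessment lies closer to the target day.

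Each such patient is worth 1.7 points at n = 60. One patient is small beside the planned half-width of 11.6 points at a 30% response rate. Three would be 3/60 = 5.0 points and five 5/60 = 8.3, but those counts are assumptions.

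Three stronger readings should be resisted:
- That the trial's primary result is inflated. The primary endpoint is continuous and analysed on observed cases (SAP 9.3), so NRI does not touch it.
- That withdrawals for lack of efficacy generally count as responses. Those with an Early Termination visit before Day 71 are missing at Week 12, and most of the others would have to meet a criterion that their withdrawal makes less likely.
- That visits after the withdrawal are always missing and so always non-response. The Week 24 window shows otherwise.

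**What to change.** In SAP 5.5.4 and 9.1, state for NRI that:

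1. A patient who permanently discontinued RPC1063 before a scheduled visit, with lack of efficacy as the primary reason, is a non-responder at that visit and onwards.
2. Where a scheduled on-treatment Week 12 or Week 52 assessment exists, it is used for that visit in preference to an Early Termination visit, even if the latter is nearer the target day. This keeps a genuine on-treatment result and prevents a conflict with item 1 in cases such as Day 82 against Day 86.
3. An Early Termination visit after such a withdrawal cannot supply a response at a later visit, including Week 24.

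SAP Appendix 5 indicates that Week 12 and Week 52 topline tables had been generated by version 1.3 and that version 1.5 followed a data review meeting. If results are known when the rule is added, introduce it by dated amendment as a sensitivity analysis, reported beside the current NRI result and not in place of it.

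Cost: wording and reprogramming. The discontinuation reason is recorded on the eCRF (Protocol 8.3) and the primary reason is already tabulated (SAP Section 6), so no new data are needed. Response rates may fall slightly. The rule would also rest on a recorded reason that is subjective in an open-label trial, so a listing of the reclassified patients should accompany it.

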9.2. Handling Endoscopy Data

9.2.1. SES-CD, GHAS, and RHI Related Endpoints

For the primary analysis of SES-CD score along with the sub-scores, only segments evaluated or imputed at both baseline and post-baseline will be summarized as described in section [5.5.5 Handling of Missing Segmental Scores for SES-CD, GHAS, and RHI](#). This will be referred to as either “Complete Case” or “Paired Segment” analysis. For example, if the rectum and left colon were evaluated at baseline and segments for the rectum, left colon, transverse colon and right colon were evaluated or imputed at Week 12, only the rectum and left colon at baseline and the rectum and left colon at Week 12 would be used to derive SES-CD and the change from baseline to Week 12 in this table.

SES-CD score will also be determined based on all available segments at a given visit without adjusting for the segments available at Baseline. These scores will be referred to as “Robarts Observed Scores”.

9.2.2. GHAS and RHI Related Endpoints (exploratory efficacy endpoints)

The sub-scores and total scores for GHAS and RHI will follow the same approach as the SES-CD related endpoints except the imputation of missing segments as they are based on the same concept of evaluating 5 segments as described above.

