	GHAS Remission	No active inflammation in any measured segment; see Appendix 4 for details
	RHI Change	RHI change from baseline
	RHI Response - by Segment	RHI segment score decrease $\geq 50\%$
	RHI Remission- by Segment	No active inflammation in a measured segment
	RHI Remission	No active inflammation in any measured segment; see Appendix 4 for details
	Global RHI Score	A weighted sum of the worst of each of the four disease components across the four colonic segments; see Appendix 4 for details
Mucosal Healing	RHI Mucosal Healing	Endoscopic Remission combined with RHI Remission
Biomarkers	CRP Change	C-reactive protein change from baseline
	CRP Response-10	C-reactive protein < 10 mg/L
	FCP Change	Fecal calprotectin change from baseline
	FCP Response-250	Fecal calprotectin < 250 mcg/g

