5.5.5. Handling of Missing Segmental Scores for SES-CD, GHAS, and RHI

The analyses of change from baseline and the defined responder analyses for SES-CD, GHAS, and RHI, as applicable, will exclude the segments non-evaluable or missing at baseline, regardless of whether or not they become evaluable post-baseline. In addition, any missing segment scores (in the presence of at least 1 non-missing segmental SES-CD score) of SES-CD will be imputed by non-missing score used in the previous visit. This methodology is the primary analysis and will also be referred to as “complete cases” or “paired segments” as only segments scored at both baseline and the repeat endoscopy will be assessed. Exploratory analyses of the SES-CD scores based on available data without any adjustments or imputation will also be performed.

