APPENDIX 4. GEBOES HISTOLOGY ACTIVITY INDEX AND ROBARTS HISTOPATHOLOGY INDEX

The following tables give details of the scoring for the Global Histologic Disease Activity Score (GHAS)^{3,4} and a newly developed scoring system entitled the Robarts Histopathology Index (RHI)⁵. Higher numbers correspond to more inflammation and mucosal damage. For each CD segment, the GHAS score can be treated as a continuous measure on a 16 point scale. For each CD segment, the RHI score can be treated as a continuous measure on a 33 point scale. Scoring for both indices will be performed for each segment (i.e., ileum, right, transverse, left (descending and sigmoid), and rectum) that is visualized and for which biopsy samples are available. Similar to the SES-CD, sub-scores for each segment will be derived.

The eight components used to assess the per-CD segment GHAS score are noted in the table below. The maximum per-CD segment total score is 16.

Table 11. GHAS Grading System

GHAS Descriptors and Levels	
Epithelial damage	0: Normal 1: Focal Pathology 2: Extensive Pathology
Architectural changes	0: Normal 1: Moderately disturbed (<50%) 2: Severely disturbed (>50%)
Infiltration of mononuclear cells in the lamina propria	0: Normal 1: Moderately increase 2: Severe increase
Infiltration of polypmorphonuclear cells in the lamina propria	0: Normal 1: Moderately increase 2: Severe increase
Polypmorphonuclear cells in epithelium	0: Normal 1: In surface epithelium 2: Cryptitis 3: Crypt abscess
Presence of erosion and/or ulcers	0: No 1: Yes
Presence of granuloma	0: No 1: Yes
Number of biopsy specimens affected	0: None (0 of 6) 1: ≤3% (1 or 2 of 6) 2: 33-66% (3 or 4 of 6) 3: >66% (5 or 6 of 6)

1

[REDACTED]

Exploratory GHAS Histologic Remission (no active inflammation in a measured segment) is defined in the following table, where the max overall GHAS score in a given segment must be less than or equal to 8, and each segment meets this standard:

Table 12. Per-CD Segment GHAS Scores Allowed for Histologic Remission

Epithelial damage	0
Architectural changes	0-2
Infiltration of mononuclear cells in the lamina propria	0-2
Infiltration of polymorphonuclear cells in the lamina propria	0
Polymorphonuclear cells in epithelium	0
Presence of erosion and/or ulcers	0
Presence of granuloma	0-1
Number of biopsy specimens affected	0-3

The four components used to assess the per-CD segment RHI score are noted in the table below. The maximum per-CD segment total score is 33.

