Table 13. Roberts Histopathology Index (RHI) Grading System

Subcomponent Descriptors	Scores	Weighting factor
Chronic inflammatory infiltrate	0=No increase 1=Mild but unequivocal increase 2=Moderate increase 3=Marked increase	1
Lamina propria neutrophils	0= None 1= Mild but unequivocal increase 2=Moderate increase 3=Marked increase	2
Neutrophils in epithelium	0=None 1 = <5% crypts involved 2= <50% crypts involved 3= >50% crypts involved	3
Erosion or ulceration	0=No erosion, ulceration or granulation tissue 1=Recovering epithelium + adjacent inflammation OR probable erosion-focally stripped 2=Unequivocal erosion 3=Ulcer or granulation tissue	5

An exploratory RHI Histologic Remission (no active inflammation in a measured segment) is defined in the following table. The maximum per-CD segment RHI score allowable for a segment to qualify for RHI Histologic Remission is 3. A patient not meeting at least one of the criteria 2, 3, or 4, below in a segment is defined as a non-RHI remitter for that segment. Note that criteria 1 is always met.

Table 14. Per-CD Segment RHI Scores Allowed for Histologic Remission

Subcomponent Descriptors	Scores	Weighting factor
Chronic inflammatory infiltrate	0-3	1
Lamina propria neutrophils	0	2
Neutrophils in epithelium	0	3
Erosion or ulceration	0	5

Global RHI Score

Global RHI Score is a weighted sum of the worst, i.e., the highest, of each of the four disease component scores across the four colonic segments, rectum, left colon, transverse colon, and right colon. Same weighting factors used in computing the RHI Score is used.

Global RHI Score = 1x highest Chronic inflammatory infiltrate score + 2x highest Lamina propria neutrophils score + 3x highest Neutrophils in epithelium score + 5x highest Erosion or ulceration score.

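### RHI and GHAS Remission are judged only on paired segments with no imputation, so a baseline-active segment not biopsied at follow-up can turn a non-remitter into a remitter

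*SAP*

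**What the plan says.** - **Definition.** SAP 4.2.1, Table 3, gives GHAS Remission and RHI Remission the same definition: "No active inflammation in any measured segment; see Appendix 4 for details". It sets no minimum number of segments and does not require every baseline segment to be sampled again.
- **What is scored.** SAP Appendix 4 scores a segment only if it is one "that is visualized and for which biopsy samples are available".
- **Pairing.** SAP 5.5.5 covers the change and responder analyses of SES-CD, GHAS and RHI, and says that "only segments scored at both baseline and the repeat endoscopy will be assessed".
- **Missing segments, SES-CD.** In the same section, a missing segment score "of SES-CD will be imputed by non-missing score used in the previous visit".
- **Missing segments, histology.** SAP 9.2.2 withholds that step: GHAS and RHI sub-scores and totals "will follow the same approach as the SES-CD related endpoints except the imputation of missing segments".
- **Missing patients.** For proportions, SAP 5.5.4 says that "patients with missing efficacy data and the responses after treatment failure will be considered non-responders (NRI) in the primary analyses". It does not mention a patient whose histology is only partly missing.

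**The concern.** Remission is an all-segments-quiet criterion. Removing a segment from such a criterion can turn a failure into a success but never the reverse, provided at least one scored segment remains. If the removed segment was the inflamed one, the missing biopsy itself produces the remission. For SES-CD the SAP guards against this by carrying the earlier score forward. For histology it does not.

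The situation is plausible. The SES-CD has a grade for a narrowing that the endoscope cannot pass, and protocol exclusion 3 removes only strictures with obstructive symptoms, so segments beyond a narrowing may not be reached. The protocol's schedule tables and section 11.1.2 speak of colonic biopsies, although the ileum is a scored segment and ileum-only disease is eligible. SAP version 1.5 added missing-segment imputation for SES-CD after a data review meeting, and no matching safeguard for histology appears.

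At stake are the reported RHI and GHAS Remission rates at Weeks 12 and 52 and, to a lesser degree, RHI Mucosal Healing. With a single arm, no control group shares the bias.

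**Working it through.** **1. The plan's own figure.** The only design numbers are the confidence-interval half-widths in SAP 5.1. The formula is 1.96 × √(p(1−p)/n).

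| n | p = 15% (remission) | p = 30% (response) |
|---|---|---|
| 30 | 12.78% | 16.40% |
| 60 | 9.03% | 11.60% |

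These match the stated 12.8 and 16.4, and 9.0 and 11.6. The SAP text names response before remission, but the first figure of each pair belongs to the 15% remission rate. The point here does not rest on these numbers; they only give a scale.

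**2. Applying the rules to a constructed patient.** RHI weights (SAP Table 13) are 1 for chronic infiltrate, 2 for lamina propria neutrophils, 3 for neutrophils in epithelium and 5 for erosion or ulceration. For remission, the last three components must all be 0 (Table 14): "The maximum per-CD segment RHI score allowable for a segment to qualify for RHI Histologic Remission is 3".

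- Baseline ileum, components 3/2/2/3: 3×1 + 2×2 + 2×3 + 3×5 = 28, which is active.
- Baseline right, transverse and left colon and rectum, components 1/0/0/0: RHI = 1 each, which is quiet.
- Baseline status: not in remission.
- Week 12: ileum not biopsied; the other four segments unchanged at 1.

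| Rule for the missing ileum | Week 12 status |
|---|---|
| SAP: paired segments, no imputation | Remitter |
| Previous score carried forward, as for SES-CD | Non-remitter |
| Missing baseline-active segment counted as failure | Non-remitter |

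No measured segment has changed, yet the patient has become a remitter. GHAS behaves in the same way, because its definition is also confined to measured segments.

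**3. What each such patient does to the rate.** The documents give neither a histologic remission rate nor a missing-biopsy rate. *Assumption, for illustration:* n = 60 and a true rate of 15%, that is 9/60. The 15% is the generic planning rate in SAP 5.1, not a histology rate. Each misclassified patient adds 1/60 = 1.7 points. Intervals are Clopper-Pearson, as in SAP 9.4.

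| Misclassified patients | Rate | 95% interval |
|---|---|---|
| 0 | 9/60 = 15.0% | 7.1–26.6% |
| 1 | 10/60 = 16.7% | 8.3–28.5% |
| 3 | 12/60 = 20.0% | 10.8–32.3% |
| 6 | 15/60 = 25.0% | 14.7–37.9% |

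Six such patients would move the estimate by 10 points, slightly more than the planned half-width of 9.0; one would move it by 1.7.

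**4. Mucosal Healing.** This endpoint also needs Endoscopic Remission: SES-CD of at most 4, a fall of at least 2, and no sub-score above 1. SAP Appendix 2 lists the sub-scores by segment. If the active segment is not reached, its earlier SES-CD score is carried forward, and a value above 1 blocks the endpoint. If it is reached and still scores above 1, that blocks it too. The main exposure is a segment that was seen, looked nearly quiet and was not biopsied.

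**The case against.** The strongest objection is that the SAP may already handle this. SAP 5.5.4 applies non-responder imputation to all proportion endpoints, and a patient lacking a baseline-active segment could be read as having missing efficacy data. Section 9.2.2 speaks of sub-scores and totals, not of remission. For GHAS, Appendix 4 adds "and each segment meets this standard". Table 6, which should list the method for each proportion endpoint, is absent from the text available for this review, so a segment rule there cannot be excluded.

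This stands as a caution but does not remove the point. Section 5.5.5 expressly covers responder analyses of GHAS and RHI and limits them to paired segments. Table 3 and Appendix 4 define remission over measured segments. The non-responder rule is written for patients, not segments. Patients with no evaluable histology and treatment failures do remain non-responders; the gap is partial missingness.

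A second objection is that the SAP already reports RHI Response and RHI Remission by segment among baseline non-remitters. That helps a careful reader but does not correct the patient-level rate.

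Two stronger readings are tempting. A reader might infer a definite bias, for example 3 to 8 points by multiplying a 10–20% chance of a missed biopsy by 30–40% of patients with exactly one unhealed segment. Nothing in the documents supports either input; biopsy procedure is in a manual outside these documents, and the missed fraction could be near zero. A reader might also infer that RHI Mucosal Healing is inflated as much as RHI Remission. SES-CD carry-forward and the sub-score limit give it substantial protection.

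**Conclusion.** The point holds on the visible SAP text. A baseline-active segment without a follow-up biopsy leaves the RHI and GHAS Remission assessment, and the patient can then be counted as a remitter with no measured improvement. The direction is certain: upward only. The size is unknown; the figures of 16.7%, 20.0% and 25.0% rest on an assumed 9/60 and assumed counts of 1, 3 and 6 patients. RHI Mucosal Healing is affected mainly through segments that were visualised and near-quiet but not biopsied. The primary endpoint, change in SES-CD, is untouched. The SAP describes the histology endpoints as exploratory and plans no hypothesis tests, so severity is low to moderate. The conclusion would fall away if Table 6 already makes such patients non-remitters.

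**What to change.** In SAP 5.5.5 and 9.2.2, state that in the primary (non-responder imputation) analysis of RHI Remission, GHAS Remission and RHI Mucosal Healing, a patient with any baseline-active segment lacking a follow-up histology score is a non-remitter. Baseline-active means failing Table 14 for RHI or Table 12 for GHAS. Keep the paired measured-segment version as the observed-case sensitivity analysis, and report at Weeks 12 and 52 how many patients the rule changes. If Table 6 already contains such a rule, bring the two sections into line with it.

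The cost is SAP wording and derivation code; no new data are needed. The downside is that a segment that truly healed but was not biopsied counts as a failure, so the primary rate is conservative and may be somewhat lower. Showing both versions makes the gap visible.
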